## I. GENERAL

Study number	f/2023/109
Title study	The effect of the stride one on the gait pattern of people after a stroke
Principal investigator	[name], M.
Client	CERITER
Protocol version number	Version 2

## II. BACKGROUND AND RATIONALE

Cerebrovascular accidents (CVA) are multifactorial disorders that affect both cognitive and physical/motor parameters. One of the most important problems in rehabilitation after CVA (due to hemiplegia) is difficulties in walking, which leads to mobility problems and dependency of the patient on others. When walking, a patient with CVA shows a clear abnormality at the level of the foot, namely an abnormal roll-off pattern. This causes the patient to compensate in other parts of the body. However, if the roll-off pattern of the foot can be influenced or improved, the patient's gait pattern will show an overall qualitative improvement. Ensuring a good foot roll-off is therefore a primary objective in gait rehabilitation after CVA.

Already on the market, Ceriter Stride One is a CE-certified medical device for qualitatively better and more independent walking. The device helps people with walking problems caused by neurological disorders such as Parkinson's disease or CVA. Stride One detects a deviating gait pattern via a smart insole and generates individually tailored audio feedback, for example to prevent or correct a deviating roll-off pattern in the foot as a result of the CVA.

To date, no extensive clinical research has been conducted with Stride One in people with a CVA. In analogy with previously published scientific literature regarding the influence of audio feedback on the gait pattern in CVA and the intensity of exercise, it is expected that Stride One will ensure a better gait pattern in this patient population (see Bibliography 1-4).

FRAME, the clinical test center of the Jessa Hospital (Belgium), was asked by CERITER to perform a Stride One clinical scientific assessment.

## **III. OBJECTIVES**

The aim of this pilot study is to investigate whether patients with a CVA show a qualitatively better gait pattern after training with a Stride One insole and whether patients can maintain this improvement in gait pattern without audio feedback at the end of the training.

Primary endpoints:

- Complete and correct foot roll-off (detected and interpreted in the accompanying software)
- Improved walking speed/greater number of steps per minute

Secondary endpoints:

- Improved functional tests: sit-to-stand, 3min walking test
- Subjective experiences: questionnaires

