## VI. METHODOLOGY

In this study, 10 subjects with impaired gait quality due to a CVA will be recruited. After signing the informed consent, the subjects will undergo baseline measurements (see outcome parameters). Subsequently, the subjects will walk with the Ceriter insole: this provides auditory feedback to the patient, stimulating/helping the patient to achieve a good foot roll-off. During the first gait training, the feedback from the insole is personalized for the patient by the head therapist and employees of Ceriter. After this first measurement/training, the patients will use the insole (+ feedback) daily during rehabilitation with a physiotherapist, as well as on their own (outside therapy) for 5 days. The same post-measurements as at baseline will take place on the last day. This will allow us to determine whether training with the Ceriter insole has a positive effect on the patient's gait pattern. Two days after the post-measurements (and without using the insole in/outside therapy) the patient will be evaluated one last time to determine whether such an intervention also has a lasting effect on the gait pattern.

In addition to the objective measurements (see timeline below), subjective questions will also be asked in the form of questionnaires. Here, the patient will be asked about his/her findings regarding the use of the sole while walking.

Goal of the therapy: to teach patients to place their feet correctly, in order to achieve a better roll-off, and therefore a better gait pattern:

- Help patients to use all areas of the foot correctly during walking
- Help patients to improve specific parts of the foot roll-off during walking
- Help patients to have a completely correct roll-off during walking
- Help patients to again walk symmetrically

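### Is gait quality judged only by a roll-off score from the device that trains it, with symmetry left unmeasured?

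*Protocol*

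**What the plan says.** The aim in section III of the protocol is to learn whether patients "show a qualitatively better gait pattern after training with a Stride One insole" and whether they keep the gain without audio feedback. The primary endpoints are "Complete and correct foot roll-off (detected and interpreted in the accompanying software") and "Improved walking speed/greater number of steps per minute". The secondary endpoints are "Improved functional tests: sit-to-stand, 3min walking test" and questionnaires on the patient's experience.

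Section II explains the device: "Stride One detects a deviating gait pattern via a smart insole and generates individually tailored audio feedback". It argues that if roll-off can be improved, the patient's "gait pattern will show an overall qualitative improvement". Section VI repeats that reasoning: patients learn to place the foot correctly "in order to achieve a better roll-off, and therefore a better gait pattern". It then lists four goals of the therapy, the last being "Help patients to again walk symmetrically".

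Measurements are taken at baseline, on the last day of a 5-day training period, and again two days later with no insole use in between. Section VIII divides the objective measurements into gait pattern and functionality, compared within subject. No control group is described.

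**The concern.** The aim concerns the quality of gait. Read strictly, only roll-off describes how the patient walks; speed, cadence and the functional tests describe how fast, or how capably. Stride One is the only system the protocol describes, so the software that reads roll-off is most naturally its own, and roll-off is also what its feedback trains. A rise in the score after training would then show that patients meet the device's criterion better. That this means better walking overall is argued in sections II and VI, and no second measure of gait quality checks it.

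Symmetry seems to be a further gap: the therapy pursues it and no endpoint records it. An analysis plan could not repair that, because it cannot supply a measurement that was never taken. With 10 patients and no control group described, what the endpoint measures largely determines what may be concluded. The danger would be a claim about gait in general that rests on a score internal to the product.

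**Working it through.** The protocol gives no figure to reproduce. The check sets endpoints against aims and counts.

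**Therapy goals (section VI).** There are four: use of all areas of the foot, improvement of specific parts of roll-off, a fully correct roll-off, and symmetrical walking.
- Covered by the roll-off endpoint: 3 of 4.
- Covered by no listed endpoint: 4 − 3 = 1, symmetry.

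**Objective quantities (section III).** There are five: roll-off, walking speed, steps per minute, sit-to-stand and the 3-minute walking test.
- Described as read by software: 1 of 5.
- Not so described: 5 − 1 = 4.

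**How many of the five count as gait pattern?** This depends on the classification.
- Strict reading, on the word qualitatively in the aim: roll-off alone, 1 of 5.
- Section VIII's own division into gait pattern and functionality: section III labels sit-to-stand and the 3-minute test functional, which leaves roll-off, speed and steps per minute as gait pattern, 3 of 5.

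The second reading uses the protocol's own categories and is at least as natural as the first. On it, the gait-pattern result does not rest on the software score alone.

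**Is symmetry a study aim?** Section III does not mention it, no hypothesis about it is stated, and section VIII does not name it. It appears only in section VI, as something the therapy tries to achieve. A therapy goal without its own endpoint contradicts nothing in a pilot of this size.

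**Does the design address coached performance?** In part. The aim includes maintenance without audio, and the last evaluation follows two days without the insole. That tests carry-over rather than response to a prompt. It does not make the score independent of the device.

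**What would an added measure require?** Filming at baseline, post-training and follow-up would give 10 × 3 = 30 recordings to rate. If the walking test is not repeated at follow-up, which section VI does not spell out, the figure is 10 × 2 = 20. Either way it needs an assessor, a rating procedure and consent to filming. Section IV reports recruitment in the past tense, for December 2023 to April 2024. Section VI uses the future tense, so timing is not certain, but the chance to film has probably passed.

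**The case for a change.** The strongest case for acting is that section III itself fixes the endpoints, so the gap cannot be left to an analysis plan. The manufacturer finances the study, its employees help to personalise the feedback, and its software appears to produce the leading endpoint. Section II concedes that no extensive clinical research with the device exists in stroke, so the step from roll-off to overall gait has little support specific to this device. Speed and cadence can rise while walking stays asymmetrical. If filming is too late, a few sentences could still confine the conclusion to roll-off as scored by Stride One.

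Much of this stands as a description. No listed endpoint measures symmetry, and no gait-quality measure is named that is clearly independent of the device. It does not carry through to a change:

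- Confining the aim to software-scored roll-off would ignore the other primary endpoint, speed or cadence.
- A ban on conclusions about symmetry would remove a conclusion the protocol never draws.
- Measuring the impairment that a therapy targets is a legitimate choice for a pilot, and section II gives the reason for choosing roll-off.
- No error in the roll-off score has been shown.

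The absence is also not fully certain. Section VI refers to outcome parameters and to a timeline that do not appear under those names in the text at hand. The first may simply mean section III; a further measure could stand in the second.

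**Conclusion.** No change to the plan. The concern is right about what is listed, but its weight depends on a narrow reading of gait quality and on treating a therapy goal as a study objective. On the protocol's own division, 3 of the 5 objective quantities describe gait pattern, and only 1 of the 5 is described as read by software. The size of any overstatement cannot be derived from the documents, and it is zero if the roll-off score reflects overall gait.

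This rests on three assumptions: that the accompanying software is Stride One's, that speed and cadence are not taken from the same score, and that the report makes no claim about symmetry. The first is the natural reading, though the protocol does not say so outright. The second fits the text but is not stated either. The third follows from the aims as written.

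The remaining limitation belongs to interpretation. Roll-off should be read as the software's score, beside speed or cadence, and its link to overall gait as a premise of the study. A careful author would report it that way without an amendment.

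### Does the protocol leave it open whether audio feedback is on or off when foot roll-off is measured?

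*Protocol*

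**What the plan says.** Section III makes roll-off a primary endpoint, read by the device's software: "Complete and correct foot roll-off (detected and interpreted in the accompanying software". It also asks "whether patients can maintain this improvement in gait pattern without audio feedback at the end of the training". Section II explains that sensing and cueing come from one product: "Stride One detects a deviating gait pattern via a smart insole and generates individually tailored audio feedback".

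Section VI sets out the sequence:

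- **Baseline, then insole walking:** "the subjects will undergo baseline measurements (see outcome parameters). Subsequently, the subjects will walk with the Ceriter insole".
- **Setting up the feedback:** "During the first gait training, the feedback from the insole is personalized for the patient by the head therapist and employees of Ceriter".
- **Transition to five days of daily use:** this opens with "After this first measurement/training".
- **Last day:** "The same post-measurements as at baseline will take place on the last day".
- **Two-day evaluation:** "Two days after the post-measurements (and without using the insole in/outside therapy) the patient will be evaluated one last time".

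None of these sentences says whether the audio is on or off during a test walk. Section VI also points to a list of outcome parameters and a timeline, neither of which appears in the text available for review. Section VIII describes a within-subject comparison before training, after training and after wash-out.

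**The concern.** Because one device both measures and cues, the audio state during a test walk is a condition of the measurement. There is no control arm, so the effect of training is read from differences between visits. If baseline were silent and the last day cued, the difference would combine what the patient learned with an immediate response to sound. If the two-day visit were then silent, the cueing part would vanish and look like lost benefit. A silent reading that was never taken cannot be recovered in the analysis.

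Two phrases add to the unease. The first session is called a measurement and a training in one breath, which could suggest that roll-off was first recorded with feedback running. And the aim refers to walking without audio, yet no test carries that label. The worry is confined to roll-off: walking speed, cadence and the functional tests can be measured without the insole.

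**Working it through.** The protocol gives no figure to reproduce here, so the check is to see which audio patterns the text allows and what each would do to the contrasts.

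**Notation.** Let L be true learning by the last day, R the share of it retained two days later, and C the immediate effect of cueing. Let a0, a1 and a2 equal 1 if audio is on at baseline, the last day and the two-day evaluation, and 0 if off. The protocol gives no values for L, R or C.

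- Last day minus baseline = L + C(a1 − a0)
- Two-day evaluation minus baseline = R·L + C(a2 − a0)

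**Step 1: no restriction.** Three visits with two states each give 2³ = 8 patterns. This counts possibilities and says nothing about how likely each is.

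**Step 2: order of events (section VI).** Baseline precedes walking with the insole, and the feedback is tailored to the patient only at the first gait training. Feedback that has not yet been set up would not be running at baseline, so a0 = 0. That leaves 2² = 4 patterns.

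**Step 3: matched tests (section VI).** The last-day measurements are the same as at baseline. Read as the same test under the same conditions, a1 = a0 = 0. Two patterns remain: off-off-off and off-off-on.

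**Step 4: last-day contrast.** In both, the gain is L + C(0 − 0) = L. Cueing contributes nothing, and the silent last-day test answers the aim of improvement without audio at the end of training.

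**Step 5: the worrying pattern.** For off-on-off with full retention (R = 1), the last-day gain is L + C and the two-day gain is L. The cueing share of the gain, and the apparent loss, are both C/(L + C). With C/L assumed at 0.25, 0.5 and 1.0:

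- 0.25/1.25 = 20%
- 0.5/1.5 = 33%
- 1.0/2.0 = 50%

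The arithmetic is right, but this pattern has a1 ≠ a0 and is excluded at step 3. The percentages do not describe the plan as it naturally reads.

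**Step 6: what stays open.** The two-day contrast is R·L if that visit is silent and R·L + C if it is cued. Relative to L, a cued visit would show R + C/L, overstating retention by 25, 50 or 100 percentage points of L for the same assumed ratios. The visit exists to see whether the effect lasts after two days without the insole, so cueing the patient during that test would defeat its purpose.

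**Step 7: the combined measurement and training phrase.** It follows a description of baseline testing and then the first training walk. Read in place, it is shorthand for a first session containing both, and it does not contradict the stated order.

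**The case for a change.** The strongest case for a change is that steps 2 and 3 are inferences. Calling the last-day measurements the same as baseline tells the reader which tests are repeated, not whether the sound is on. The last day closes a period of daily use with feedback, so a cued reading could happen in practice. The instruction not to use the insole governs therapy during the two-day interval and does not say how the software reads roll-off at the visit itself, which appears to require wearing the insole. Conditions of measurement have to be set before the test walk, so no later analysis plan can supply them. A sentence in section VI would cost almost nothing.

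Part of this stands. The audio state is indeed unwritten at all three assessments, and the two-day evaluation has the least support from surrounding text. But the case shows an unstated condition and no mismatch. Two matched audio-on tests would require feedback at baseline, against the described order. The outcome list and timeline that section VI refers to are not available, and they are where such conditions would usually be given, so their absence here cannot count as a defect. Section IV also reports recruitment between December 2023 and April 2024 in the past tense, although section VI is in the future tense. If the data are already collected, new protocol wording could not alter how they were recorded.

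**Conclusion.** The concern does not call for a change. The plan omits a detail that a sensible team fills in correctly from the sequence it describes: a silent baseline, the same silent test on the last day, and a silent evaluation after the wash-out. On that reading the distortion is zero in both contrasts. The remaining exposure is at the two-day evaluation alone, and it would arise only if that test were cued against its own purpose.

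The conclusion rests on three assumptions: that feedback is not running before it has been personalised, that the same measurements means the same conditions, and that the insole can record without sounding, which the protocol does not state. If the unseen outcome list or timeline specified different audio states across visits, the question would reopen. For a 10-patient pilot whose data are to be analysed and displayed in aggregate, with no stated rule that gives a wrong answer when followed, this is a point of clarity and not an error in the plan.

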#### **IV. STUDY POPULATION**

In the context of this pilot study, 10 patients with a CVA were recruited between December 2023 and April 2024 from the rehabilitation center of the Jessa hospital (campus Sint-Ursula) in Herk-de-Stad, Belgium, using the following criteria:

Inclusion criteria:

- CVA, residentially admitted to the rehabilitation center
- Older than 18 years of age
- Gait problems as a result of the CVA
- Able to walk safely and independently (possibly with a walking aid)
- Able to understand and sign an information and consent form

Exclusion criteria:

- Severe cognitive problems (attention) that make it difficult to understand instructions or follow feedback
- Hearing problem

The study was approved by the Jessa Hospital Medical Ethics Committee (2023/c/109).

#### V. RECRUITMENT AND INFORMED CONSENT

Potential participants for this study will be identified by the head of the paramedic department and his team of therapists. Participants consist of patients who have been admitted to the rehabilitation center of Herk-de-Stad, Belgium as a result of a CVA.

If the head of the paramedic or one of the members of his team finds a suitable candidate (impaired gait pattern due to CVA), who they think is suitable for participation in the study, the therapist will approach the patient him/her self to ask whether he or she is interested in participating in the study. After this, the local researcher will approach the patient with an informed consent and additional explanation about the study. After the local researcher has received confirmation from the patient through oral questioning that all information is clear, the informed consent will be signed. As stated in the informed consent, the patient can withdraw from the study at any time, without further consequences.

## VI. METHODOLOGY

In this study, 10 subjects with impaired gait quality due to a CVA will be recruited. After signing the informed consent, the subjects will undergo baseline measurements (see outcome parameters). Subsequently, the subjects will walk with the Ceriter insole: this provides auditory feedback to the patient, stimulating/helping the patient to achieve a good foot roll-off. During the first gait training, the feedback from the insole is personalized for the patient by the head therapist and employees of Ceriter. After this first measurement/training, the patients will use the insole (+ feedback) daily during rehabilitation with a physiotherapist, as well as on their own (outside therapy) for 5 days. The same post-measurements as at baseline will take place on the last day. This will allow us to determine whether training with the Ceriter insole has a positive effect on the patient's gait pattern. Two days after the post-measurements (and without using the insole in/outside therapy) the patient will be evaluated one last time to determine whether such an intervention also has a lasting effect on the gait pattern.

In addition to the objective measurements (see timeline below), subjective questions will also be asked in the form of questionnaires. Here, the patient will be asked about his/her findings regarding the use of the sole while walking.

Goal of the therapy: to teach patients to place their feet correctly, in order to achieve a better roll-off, and therefore a better gait pattern:

- Help patients to use all areas of the foot correctly during walking
- Help patients to improve specific parts of the foot roll-off during walking
- Help patients to have a completely correct roll-off during walking
- Help patients to again walk symmetrically

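### Section VI promises to determine a positive and a lasting effect of the insole, but one group measured before and after training alongside rehabilitation cannot attribute the change to the insole

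*Protocol*

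**What the plan says.** Section VI of the protocol describes one group of 10 subjects. Each has baseline measurements, uses the insole with feedback for 5 days, repeats the measurements on the last day, and is evaluated once more two days later. The insole is not a stand-alone treatment: "the patients will use the insole (+ feedback) daily during rehabilitation with a physiotherapist", and patients also use it on their own.

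Two conclusions are attached to these visits. On the baseline-to-post comparison: "This will allow us to determine whether training with the Ceriter insole has a positive effect". On the visit two days later, its purpose is "to determine whether such an intervention also has a lasting effect on the gait pattern". For those two days Section VI rules out the insole both in therapy and outside it.

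On the population, Section IV requires "CVA, residentially admitted to the rehabilitation center", and Section V says: "Participants consist of patients who have been admitted to the rehabilitation center of Herk-de-Stad, Belgium as a result of a CVA".

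Section III is more careful. It sets out to "investigate whether patients with a CVA show a qualitatively better gait pattern after training with a Stride One insole", and to see whether the improvement is kept without audio feedback. Section VIII calls the study a pilot with a within-subject comparison before training, after training and after wash-out, but still speaks of seeing whether the intervention has an effect.

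**The concern.** Determining that training with the insole has a positive effect is a causal conclusion. It needs some account of what these patients would have done over the same days without the insole. The text available gives none: no control group, no insole without feedback, no repeated baseline and no historical reference. Nor does it acknowledge other causes of change, although physiotherapy is part of the training period by design.

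If the two sentences stand, an improvement, or its presence two days later, could be reported as caused by Stride One. There is little direct evidence against which to check such a claim. Section II says: "To date, no extensive clinical research has been conducted with Stride One in people with a CVA". No statistical analysis plan could repair this, because the missing element is a comparator and not a method.

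**Working it through.** The protocol gives no effect size, standard deviation, test or sample size calculation for this question, so there is no figure to reproduce. The check is whether the planned measurements can separate the sources of change.

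**Inputs.**
- One group of 10, all given the insole (Section VI).
- Three time points: baseline, last day of 5 days' use, and two days later without the insole (Section VI).
- Physiotherapy alongside the insole (Section VI), in residential patients (Section IV) admitted because of a CVA (Section V).
- Therapy in the last two days: Section VI excludes the insole in therapy as well as outside it. That implies therapy continues and only the insole is withdrawn.

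**Components of mean change.**
- e = insole effect at the end of training
- g = background gain during training (rehabilitation, recovery, familiarity with the tests)
- k = insole effect still present two days later
- h = background change over those two days

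**What the study observes.**
- Baseline to post: y1 = e + g
- Post to two days later: y2 = (k − e) + h

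That is two equations in four unknowns. The coefficient matrix [[1, 1, 0, 0], [−1, 0, 1, 1]] has rank 2. A larger sample would estimate y1 and y2 more precisely but would not separate e from g.

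**Gain of 1 unit, fully kept (y1 = 1, y2 = 0).** Each of these reproduces it:
- All insole, (e, g, k, h) = (1, 0, 1, 0): y1 = 1 + 0 = 1; y2 = 1 − 1 + 0 = 0.
- All background, (0, 1, 0, 0): y1 = 0 + 1 = 1; y2 = 0 − 0 + 0 = 0.
- Half each, (0.5, 0.5, 0.5, 0): y1 = 0.5 + 0.5 = 1; y2 = 0.5 − 0.5 + 0 = 0.

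**Gain of 1 unit, fully lost (y1 = 1, y2 = −1).**
- Insole effect that disappears, (1, 0, 0, 0): y1 = 1; y2 = 0 − 1 + 0 = −1.
- Pure background, (0, 1, 0, −1): y1 = 1; y2 = 0 − 0 − 1 = −1. The whole background gain would have to reverse in two days while therapy continues.

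The second account is strained but not excluded, so a loss is weak evidence that the insole contributed. On the insole reading k = 0, which is the opposite of a lasting effect.

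A kept gain therefore does not identify the insole, and a lost gain argues against persistence. Neither result determines a lasting insole effect.

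**The case against.** **It is a declared pilot, and the analysis is only descriptive.** This is largely fair. A single-group pilot is a legitimate design, Section VIII names no test or threshold, and the aim in Section III is temporal. But the pilot label does not withdraw the two statements in Section VI, so the wording remains wrong.

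**The two-day visit does carry information.** This stands in part. A reader might infer that the visit is useless, or that insole and background explain a kept gain equally well. The protocol supports neither reading. If background gain ran at a steady rate over 5 days (an assumption), a pure background gain of 1 would lead one to expect a further 2/5 × 1 = 0.4 over the next two days, and a plateau would count somewhat against it. Test familiarity or noise could still produce a plateau. The components remain unidentified, but the explanations are not equally plausible.

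**A comparator may be in missing text.** Section VI points to outcome parameters and a timeline that are not in the text available. They could hold repeated baselines or measurements with and without feedback. That is possible but nothing shows it, and the within-subject comparison in Section VIII makes an undescribed control group unlikely.

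**There is other evidence.** Section II does cite published work on audio feedback after CVA as the basis for its expectation. That is indirect support, and it cannot replace a comparator in this study.

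**The practical gain is small.** Section IV says "10 patients with a CVA were recruited between December 2023 and April 2024", while Section VI puts recruitment in the future. If recruitment is complete, rewording the protocol matters less and the report matters more.

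**Conclusion.** The two statements in Section VI claim something the design cannot deliver, and should be corrected. The effect wording in Section VIII has the same fault in softer form.

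The point is logical: two observed mean changes, four unknown components. It rests on the absence of a comparator in the text available, and on therapy running alongside the insole. That therapy continues in the last two days is implied by Section VI, not stated outright.

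A reader might also want to attach a false-positive rate. The protocol gives no test, significance level, standard deviation or background gain, and does not state time since the CVA, so any such rate would rest wholly on assumptions. Nor does it follow that the study should not run or that its aim must change. Better gait after training, and its maintenance without audio feedback, can be described with these data. What cannot be concluded is that Stride One caused either.

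**What to change.** **Section VI.** Replace the sentence that promises to determine a positive effect with: *The baseline-to-post comparison describes the change in gait pattern during rehabilitation plus Stride One training.* Keep the two-day visit, but give its purpose as: *to describe whether that change is still present after two days without the insole. Without a comparator, neither the change nor its persistence can be attributed to Stride One alone.*

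**Section VIII.** Replace the phrase about seeing whether the intervention has an effect with: *to describe within-patient change, during rehabilitation plus Stride One, in* the objective measurements.

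**Study report.** State the same limit, and read the word effect in the study title in that sense. Leave the aim in Section III as worded.

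**Cost.** Wording only: no added patients, visits or tests. Section IV records ethics approval, so changing the protocol may need an amendment; if recruitment is complete, the statement in the report suffices. The real cost falls on the sponsor, who could not cite this pilot alone as evidence that Stride One caused an improvement. Attribution would need a later controlled study.
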